### **3.1.4 Timing of Samples for PK, Viral Load, and NS1**

The timing of samples for PK analyses, viral load determination, and NS1 levels are outlined below for TID and for BID dosing. As shown in the tables below, the timing will vary depending on the time of day that the patient received Dose 1 of study medication and how many doses of study medication they received on Day 1.

10. Timing of sample collections for patients who begin TID dosing at different times on Day 1 and thus receive either 3 doses, 2 doses, or 1 dose of study medication on Day 1, are provided in [Table 3-2](#), [Table 3-3](#), and [Table 3-4](#), respectively. In these tables, Day 1 is the day of dosing. Some of the PK sample times are fixed (pre-dose on Day 1, 24 hours after Dose 1), and some are flexible (serial PK samples for TID dosing may be obtained at either dose 7, 8, or 9). Some of the virology sample times are fixed (pre-dose on Day 1, 24 hours after Dose 1, 48 hours after Dose 1, and 8-24 hours after Dose 15). Other virology sample times are flexible, with samples collected anytime on each of 6 days (Days 4, 5, 7, 8, 14, and 28).
11. Timing of sample collections for patients who begin BID dosing at different times on Day 1 and thus receive either 2 doses or 1 dose of study medication on Day 1, are provided in [Table 3-5](#) and [Table 3-6](#), respectively. In these tables, Day 1 is the day of dosing. Some of the PK sample times are fixed (pre-dose on Day 1, 24 hours after Dose 1), and some are flexible (serial PK samples for BID dosing may be obtained at either dose 5, 6, or 7). Some of the virology sample times are fixed (pre-dose on Day 1, 24 hours after Dose 1, 48 hours after Dose 1, and 8-24 hours after Dose 10). Other virology sample times are flexible, with samples collected anytime on each of 6 days (Days 4, 5, 7, 8, 14, and 28).

**Table 3-2 TID dosing beginning before 10 AM, with 3 doses given on Day 1: Timing of samples for PK, viral load, and NS1**

For TID Dosing (with 3 doses given on Day 1)			
Day	Dose #	PK draw	Viral load and NS1
Day 1	1	Predose	Predose
	2		
	3		
Day 2	4	24 hrs post Dose #1	24 hrs post Dose #1 (prior to Dose #4)
	5		
	6		
Day 3	7	Predose #7 AND 0.5, 1, 2, 4, and 6 hrs post dose #7  NOTE: Serial PK can be done at Dose 7, 8, or 9 (based on site/patient convenience).	48 hrs post Dose #1 (prior to Dose #7)
	8		
	9		
Day 4	10		One sample anytime Day 4
	11		
	12		
Day 5	13		One sample anytime Day 5
	14		
	15		
Day 6			8-24 hrs post Dose #15
Day 7			Any time
Day 8			Any time
Day 14			Any time
Day 28			Any time

**Table 3-3 TID dosing beginning between 10 AM and 4 PM, with 2 doses given on Day 1: Timing of samples for PK, viral load, and NS1**

For TID Dosing (with 2 doses given on Day 1)			
Day	Dose #	PK draw	Viral load and NS1
Day 1	1	Predose	Predose
	2		
Day 2	3	24 hrs post Dose #1 (prior to Dose #4)	24 hrs post Dose #1 (prior to Dose #4)
	4		
	5		
Day 3	6	Predose #7 AND 0.5, 1, 2, 4, and 6 hrs post dose #7  NOTE: Serial PK can be done at Dose 7, 8, or 9 (based on site/patient convenience).	48 hrs post Dose #1 (prior to Dose #7)
	7		
	8		
Day 4	9		One sample anytime Day 4
	10		
	11		
Day 5	12		One sample anytime Day 5
	13		
	14		
Day 6	15		8-24 hrs post Dose #15
Day 7			Any time
Day 8			Any time
Day 14			Any time
Day 28			Any time

**Table 3-4 TID dosing beginning in the evening, with 1 dose given on Day 1:  
 Timing of samples for PK, viral load, and NS1**

For TID Dosing (with 1 dose given on Day 1)			
Day	Dose #	PK draw	Viral load and NS1
Day 1	1	Predose	Predose
Day 2	2		
	3		
	4	24 hrs post Dose #1 (prior to Dose #4)	24 hrs post Dose #1 (prior to Dose #4)
Day 3	5		
	6		
	7	Predose #7 AND 0.5, 1, 2, 4, and 6 hrs post dose #7	48 hrs post Dose #1 (prior to Dose #7)
Day 4	8	NOTE: Serial PK can be done at Dose 7, 8, or 9 (based on site/patient convenience).	One sample anytime Day 4
	9		
	10		
Day 5	11		One sample anytime Day 5
	12		
	13		
Day 6	14		
	15		
			8-24 hrs post Dose #15
Day 7			Any time
Day 8			Any time
Day 14			Any time
Day 28			Any time

**Table 3-5 BID dosing beginning before 4 PM, with 2 doses given on Day 1:  
 Timing of samples for PK, viral load, and NS1**

For BID Dosing (with 2 doses given on Day 1)			
Day	Dose #	PK draw	Viral load and NS1
Day 1	1	Predose	Predose
	2		
Day 2	3	24 hrs post Dose #1 (prior to Dose #3)	24 hrs post Dose #1 (prior to Dose #3)
	4		
Day 3	5	Predose #5 AND 0.5, 1, 2, 4, 6, and 8 hrs post dose #5 NOTE: Serial PK can be done at Dose 5, 6 or 7 (based on site/patient convenience.)	48 hrs post Dose #1 (prior to Dose #5)
	6		
Day 4	7		One sample anytime Day 4
	8		
Day 5	9		One sample anytime Day 5
	10		
Day 6			8-24 hrs post Dose #10
7			Any time
8			Any time
14			Any time
28			Any time

**Table 3-6 BID dosing beginning between 6 PM and 10 PM, with 1 dose given on Day 1: Timing of samples for PK, viral load, and NS1**

For BID Dosing (with 1 doses given on Day 1)			
Day	Dose #	PK draw	Viral load and NS1
Day 1	1	Predose	Predose
Day 2	2		
	3	24 hrs post Dose #1 (prior to Dose #3)	24 hrs post Dose #1 (prior to Dose #3)
Day 3	4		
	5	Predose #5 AND 0.5, 1, 2, 4, 6 and 8 hrs post dose #5	48 hrs post Dose #1 (prior to Dose #5)
Day 4	6	NOTE: Serial PK can be done at Dose 5, 6 or 7 (based on site/patient convenience.	One sample anytime Day 4
	7		
Day 5	8		One sample anytime Day 5
	9		
Day 6	10		8-24 hrs post Dose #10
Day 7			Any time
Day 8			Any time
Day 14			Any time
Day 28			Any time

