- h. Pharmacokinetic (PK) plasma samples will be collected on Day 1 at time 0 (pre-dose; before the first dose on Day 1) and 24 hours after Dose 1. For TID dosing, samples will be obtained before Dose 7 and 0.5, 1, 2, 4, and 6 hours after Dose 7. This serial PK sampling for TID dosing may be done for Dose 7, 8, or 9, based on site/patient convenience. For BID dosing, samples will be obtained before Dose 5 and 0.5, 1, 2, 4, 6, and 8 hours after Dose 5. This serial PK sampling for BID dosing may be done for Dose 5, 6, or 7, based on site/patient convenience. For blood samples, a ± 10-minute window for time points ≤4 hours; ± 15 minute for time points between 4 and 24 hours. PK samples will also be obtained at any early study discontinuation visits. The timing of these PK samples relative to the last 2 (most recent) doses will be recorded. See [Section 3.1.4](#).
- i. Subjects can begin treatment with study drug before the DENV-serotype results are obtained.

- 
- j. Measurement of plasma viremia by viral titre and using a serotype-specific, real-time reverse transcription polymerase chain reaction (RT-PCR) assay. Subjects can begin treatment before the viral load results are obtained. See [Section 3.1.4](#) for details about the timing of this assay.
- k. Adverse events are collected beginning at screening. Treatment-emergent adverse events and serious adverse events will be assessed from the time of study drug dosing until end of study and should be followed until they are resolved, stable, or judged by the investigator to be not clinically significant.
- l. After subjects are confirmed eligible at screening, randomization and the initial dosing should occur within 24 hours, the initial dose should be given on the same day as screening, if possible. TID dosing at screening/Day 1 can begin in the morning, at mid-day, or in the evening (see [Section 3.1.2](#). BID dosing on Screening/Day 1 can begin in the morning or the evening (See [Section 3.1.3](#)).  
Note that if the initial dose of study drug is administered on the same day as screening (at mid-day or in the evening), the last dose(s) of study drug will be administered on Day 6.
- 

### 3.1.1 Screening/Day 1

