### **3.1.3 Timing of BID Dosing**

If possible, the first dose of study medication should be administered on the same day as screening.

The first dose of study medication (on Day 1) must be taken under observation at the study site. The doses for PK evaluation (for Dose 5, 6, or 7; see Section 3.1.4) must also be taken under observation at the study site, or under observation by mobile nursing staff as applicable.

All other doses may be administered either at the study site or will be self-administered outside the study site (e.g., at home). The timing of the doses will be recorded in a patient diary.

The second dose of study medication must be taken after at least 6 hours and no later than 12 hours after the first dose, allowing the participant to select a convenient 12-hour ( $\pm 2$  hours) dosing schedule thereafter to complete a total of 10 doses. For example,

- If the first dose of study medication is administered between 6AM and 1 PM on Day 1, the second dose should be administered between 6 PM and no later than 10PM on Day 1, and then the subject can begin their preferred 12-hour dosing schedule on Day 2 (e.g., 6 AM and 6 PM, OR 7 AM and 7 PM, OR 8 AM or 8 PM, etc.), as long as the 12 hours ( $\pm 2$  hours) timing of doses is adhered to.
- Or if the first dose of study medication is administered between 1 PM and 4 PM on Day 1, the second dose should be administered at 10 PM on Day 1, and then the subject can begin their preferred 12-hour dosing schedule on Day 2 (eg, 6 AM and 6 PM, OR 7 AM and 7 PM, OR 8 AM or 8 PM, etc), as long as the 12 hours ( $\pm 2$  hours) timing of doses is adhered to.
- Or if the first dose of study medication is administered between 6 PM and 10 PM on Day 1, the subject can then begin their preferred 12-hour dosing schedule on Day 2

(e.g., 6 AM and 6 PM, OR 7 AM and 7 PM, OR 8 AM or 8 PM, etc.), as long as the 12 hours ( $\pm 2$  hours) timing of doses is adhered to.

Doses of study drug should be separated by 12 hours ( $\pm 2$  hours). After Day 1, if a dose is delayed, it should be taken as soon as possible, but must be taken at least 6 hours before the next scheduled dose. Otherwise, the dose must be skipped, and the next dose taken as scheduled. Dosing will be stopped at the end of the 10-dose treatment period. At the end of the treatment period, the tablets from any missed doses should be returned to the site.

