### 6.2 SECONDARY ENDPOINTS: PHARMACOKINETIC ENDPOINTS

- Plasma concentrations of AT-281 (and metabolites AT-551, AT-229, AT-219, and AT-273) for each cohort at the following timepoints:
  - Day 1: Pre-dose (before the first dose, time 0)
  - 24 hours after Dose 1 (before Dose 4 for TID dosing and before Dose 3 for BID dosing)
  - A day of intensive PK sampling:
    - i. For TID dosing, samples will be obtained before Dose 7 and 0.5, 1, 2, 4, and 6 hours after Dose 7. This serial PK sampling may be done for Dose 7, 8, or 9, based on site/patient convenience
    - ii. For BID dosing, samples will be obtained before Dose 5 and 0.5, 1, 2, 4, 6, and 8 hours after Dose 5. This serial PK sampling may be done for Dose 5, 6, or 7, based on site/patient convenience

For blood samples (both TID and BID dosing), a  $\pm 10$ -minute window for time points  $\leq 4$  hours;  $\pm 15$  minute for time points between 4 and 24 hours

  - At any early study discontinuation visits. The timing of these PK samples relative to the last 2 (most recent) doses will be recorded
- Noncompartmental analysis will be performed for the following plasma PK parameters, when applicable and if data permit. Other PK parameters may also be calculated. PK parameters, where applicable, will be calculated based on actual times:
  - $AUC_{last}$  (area under the plasma concentration versus time curve from time 0 to the last quantifiable concentration)
  - $AUC_{tau}$  (area under the plasma concentration versus time curve over the dosing interval)

- $AUC_{inf}$  (area under the plasma concentration versus time curve from time 0 to extrapolated to infinity)
- $C_{max}$
- $T_{max}$
- $t_{1/2z}$  (apparent terminal elimination half-life)
- CL/F for AT-281 only (apparent oral clearance)
- $V_z/F$  for AT-281 only (apparent volume of distribution)
- $C_{trough}$

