## 11. Pharmacokinetics

Plasma PK concentrations for CCI, AT-551, AT-229, AT-219 and AT-273 will be summarized for each nominal scheduled collection time. Summaries will include descriptive statistics (number of subjects, arithmetic mean, SD, coefficient of variation (CV), geometric mean, geometric CV, median, minimum, and maximum) and the number/percentage of samples reported as below the limit of quantification (BLQ).

All PK listings and individual concentration-time profiles will be presented for the AT-752 treated safety population. Plasma concentration versus actual time profiles for each subject will be presented graphically by treatment using a semi-logarithmic scale. The mean plasma concentration versus scheduled time profiles will be presented graphically by treatment using a semi-logarithmic scale.

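### For BID first doses after noon and up to 4 PM, the 24-hour PK sample cannot also precede Dose 3, and the SAP does not say how to summarise it

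*Protocol*

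**What the plan says.** Protocol Section 6.2 names the concentration at "24 hours after Dose 1 (before Dose 4 for TID dosing and before Dose 3 for BID dosing") as a secondary PK endpoint. For BID, Table 3-5 repeats this as "24 hrs post Dose #1 (prior to Dose #3"), and Table 3-6 carries the same condition for evening starts. For TID, Tables 3-3 and 3-4 give "24 hrs post Dose #1 (prior to Dose #4"). In Table 3-2 only the virology column has the bracket, but Section 6.2 applies the condition to every TID PK sample.

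The time is not flexible. Section 3.1.4 states: "Some of the PK sample times are fixed (pre-dose on Day 1, 24 hours after Dose 1"). Footnote h of Table 3-1 allows a window of plus or minus "15 minute for time points between 4 and 24 hours".

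Section 3.1.3 sets the BID doses on Day 1. For a first dose from 6 AM to 1 PM, Dose 2 falls "between 6 PM and no later than 10PM on Day 1". For a first dose "between 1 PM and 4 PM on Day 1, the second dose should be administered at 10 PM on Day 1". Dose 2 may come no more than 12 hours after Dose 1, and doses are 12 hours apart, give or take 2.

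SAP Section 11 says that plasma concentrations "will be summarized for each nominal scheduled collection time". It has no rule for a 24-hour sample drawn after the next dose.

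**The concern.** The sample has two definitions, one by elapsed time and one by dose order. The Day 1 rules shorten the first intervals so that patients can move to a convenient schedule on Day 2. A shortened interval brings the next dose forward and leaves the 24-hour point where it was, so for some start times the named dose comes first.

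A site then has to break one condition. If it keeps the clock time, it draws after the dose. If it keeps the dose order, it draws early and outside the window. The SAP would put either result in the 24-hour row. This is the only scheduled PK sample between the Day 1 pre-dose draw and the serial-sampling day, and each cohort has only 15 subjects on active drug, so a few post-dose values can move the summary.

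**Working it through.** The plan gives no figure to reproduce. The check compares clock times under the protocol's own rules.

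**BID inputs (Section 3.1.3).** Dose 2 comes at most 12 h after Dose 1 and, for daytime starts, by 10 PM. Dose 3 comes 10 to 14 h after Dose 2. The sample is at Dose 1 + 24 h, or + 23.75 h at the early edge of the window.

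Latest Dose 3 = latest Dose 2 + 14 h. Both conditions can be met only if (latest Dose 3 − Dose 1) is at least 24 h, or 23.75 h using the window.

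| Dose 1 | Latest Dose 2 | Latest Dose 3 (Day 2) | Hours after Dose 1 | Both conditions possible? |
|---|---|---|---|---|
| 6 AM | 6 PM | 8 AM | 26 | yes |
| 10 AM | 10 PM | noon | 26 | yes |
| 11 AM | 10 PM | noon | 25 | yes |
| noon | 10 PM | noon | 24 | at the limit |
| 12:15 PM | 10 PM | noon | 23.75 | only with the full window |
| 1 PM | 10 PM | noon | 23 | no |
| 2 PM | 10 PM | noon | 22 | no |
| 3 PM | 10 PM | noon | 21 | no |
| 4 PM | 10 PM | noon | 20 | no |
| 6–10 PM | 6–10 AM, Day 2 | 8 PM–midnight | 26 | yes |

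- Hours that fail: noon to 4 PM = 4 h, or 12:15 PM to 4 PM = 3.75 h with the window.
- Permitted BID start hours: 6 AM–4 PM (10 h) plus 6–10 PM (4 h) = 14 h.
- Share: 4/14 = 29% of all BID start hours, or 4/10 = 40% of those covered by Table 3-5.
- Position of the draw: after a 10 PM Dose 2, Dose 3 falls between 8 AM (+10 h) and noon (+14 h). For a 1–4 PM start, a draw kept at 24 h is therefore from 1 h (1 PM − noon) to 8 h (4 PM − 8 AM) after Dose 3.
- Illustration in subjects: the documents do not give the spread of start times. If starts were even over all 14 h, 15 × 4/14 = 4.3 of 15 active subjects in a BID cohort would be affected. If all starts were in the daytime and even over those 10 h, the figure is 15 × 4/10 = 6. If nobody starts after noon and before 4 PM, it is 0.

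**TID, printed example (Section 3.1.2; schedule 6 AM, 2 PM, 10 PM).** For a start from 8 to 10 AM, Dose 2 is at 4 PM, Dose 3 at 10 PM and Dose 4 at 6 AM on Day 2, or 8 AM with the 2 h allowance. The sample is due between 8 and 10 AM. Every start after 8 AM (after 8:15 AM using the window) therefore has its sample after Dose 4. Starts from 6 to 8 AM and from 2 to 4 PM miss the dose order if doses are exactly on time, but fit with the 2 h allowance.

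**TID, any permitted schedule.** Section 3.1.2 allows gaps of 6 to 10 h on a schedule that the participant chooses. With three doses on Day 1, Dose 3 can be as late as midnight and Dose 4 as late as 10 AM on Day 2. That is 28, 26 and 24 h after starts at 6, 8 and 10 AM. For the other starts a search over all gaps gives a latest Dose 4 of 28 to 30 h. No TID start is strictly impossible.

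**The case against.** **The draw-before-dose rule.** Protocol Section 5.1 has study drug given after the blood draw when a morning draw is required, which might seem to settle the order. It does not cover the BID cases, whose draws fall in the afternoon. In the printed TID example, holding Dose 4 until after a draw later than 8 AM makes the gap from the 10 PM Dose 3 longer than 10 h and leaves less than 6 h before the 2 PM dose. It would break two other rules.

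**The late-dose rule.** After Day 1 a delayed dose may be taken up to 6 h before the next scheduled one. On an 8 AM/8 PM schedule that would let Dose 3 move to 2 PM. But 2 PM is 16 h after a 10 PM Dose 2, outside the 12 ± 2 h separation. This reading does not remove the conflict.

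**Readings that go too far.** A reader might infer that TID dosing in general cannot satisfy both conditions. The documents do not support that: the 6 AM/2 PM/10 PM times are an example, and other permitted schedules work. Nor do TID starts between 10 AM and noon conflict: in the example their sample falls 4 to 6 h after Dose 3 and before the 2 PM Dose 4.

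A reader might also infer that trough exposure is contaminated. No document calls the 24-hour value a trough. SAP Section 11.2 takes Ctrough from the sample before Dose 7 (TID) or Dose 5 (BID), and estimates PK parameters from actual times. Individual profiles also use actual time. What stands is that the effect is confined to one descriptive row, and that mixing occurs only where sites keep the 24-hour time.

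**Conclusion.** The contradiction is real and narrow. For BID first doses after noon (after 12:15 PM with the window) up to 4 PM, no schedule meets both conditions: 4 of 14 permitted start hours, or 3.75 with the window. This affects Cohort 3, and Cohort 2 if it is dosed BID. The printed TID example fails for starts after 8 AM up to 10 AM, which concerns only patients who follow that schedule.

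The consequence is minor. The 24-hour row of a named secondary PK endpoint can pool pre-dose and post-dose concentrations in proportions set by clinic hours. The primary PK parameters drawn from serial sampling, and Ctrough, do not change. I put no factor on the concentration difference, because the documents reviewed give no half-life from which to compute one.

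This rests on applying the 12 ± 2 h separation to the interval from Dose 2 to Dose 3, and on reading the 15-minute window as including the 24-hour point. The shares are of clock hours, not of patients.

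**What to change.** In SAP Section 11, add a derivation for the 24-hour sample. From the recorded dose and sample times, classify each sample as taken before or after the named dose (Dose 3 for BID, Dose 4 for TID). Summarise the two groups in separate rows, and report time since last dose for each.

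The protocol statements on sample time and dose order must be reconciled: Sections 3.1.2 and 3.1.3 (dose timing), Section 3.1.4 with Tables 3-2 to 3-6, footnote h of Table 3-1, Section 5.1 (draw before dose) and Section 6.2. The virology columns carry the same dose-order condition at 24 and 48 hours and should be read in the same pass. Which condition should give way is for the sponsor to decide.

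The cost is small. Protocol Section 5.5 already records the date and time of each dose, and SAP Section 11.2 already uses actual sampling times, so no new data are needed. The downside is fewer values in each summary row.

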#### 4. STUDY POPULATION

Approximately 60 subjects will be enrolled in the study at approximately 40 study sites. Subjects will be adults with confirmed DENV infection.

##### 4.1 INCLUSION CRITERIA

A patient must meet the following criteria to be eligible for participation in this study:

1. 18-55 years of age at time of screening
2. Fever  $\geq 38^{\circ}\text{C}$  (or feeling feverish) with onset during the previous 60 hours
3. Positive test confirming DENV on a NS1 antigen test or RT-PCR assay
4. Negative rapid diagnostic test results for SARS-CoV-2 and Influenza A and B
5. Body mass index (BMI) of 18 to 30  $\text{kg/m}^2$

6. Provides written informed consent prior to initiation of any study procedures
7. Able to understand and agrees to comply with planned study procedures and be available for all study visits
8. Males and females of childbearing potential must agree to use protocol-specified methods of contraception as described in [Section 4.1.1](#)
9. Male subjects must agree to not donate sperm from the first dose through 90 days after the last dose of study drug

#### **4.1.1 Protocol Specified Methods of Contraception**

- Female subjects of childbearing potential must agree to use one of the following methods of birth control from screening through 30 days after the last dose of study drug:
  - intrauterine device (IUD)
  - bilateral tubal occlusion
  - vasectomized partner
  - sexual abstinence
  - hormonal contraception (including combined, progesterone only or intrauterine hormone-releasing system [IUS]) together with a barrier method such as (i) male or female condom with or without spermicide or (ii) cap, diaphragm or sponge with spermicide

Note: A female subject of non-childbearing potential is defined as a female  $\geq 54$  years old with menses cessation for  $\geq 12$  months since previous menses, or a female of any age who had a hysterectomy, bilateral oophorectomy, or bilateral tubal ligation.

- Male subjects must agree to use a condom from the first dose through 90 days after the last dose of the study drugs. If their female partner is of childbearing potential, the male subject must agree to discuss with his female partner the importance of using one of the additional contraceptive methods listed above from the first dose through 90 days after the last dose of study drug.
- Male subjects must have agreed not to donate sperm from the first dose through 90 days after the last dose of study drug.

#### **4.2 EXCLUSION CRITERIA**

A patient who meets any of the following criteria will be excluded from participation in this study:

1. Pregnant at screening or plans to become pregnant within 90 days of screening
2. Female patient who is breastfeeding or plans to breastfeed during the study period
3. Has previously received any investigational or approved vaccine for dengue
4. Previous history of HIV, active chronic hepatitis B infection, or current hepatitis C infection (from medical history)
5. Use of any antiviral drug within 30 days or within 5 half-lives (whichever is longer) of the active drug or metabolite (for long-acting antivirals) of screening
6. Currently enrolled in or plans to participate in another clinical trial with an investigational agent or device that will be received during the study-reporting period
7. Exposure to another investigational agent within 30 days or 5 half-lives, whichever is longer, prior to study drug administration
8. Concomitant use of herbal or natural supplements or grapefruit juice (e.g. St. John's Wort, echinacea, milk thistle) or grapefruit juice. These should be discontinued at screening if the investigator feels that they can be safely discontinued or substituted for the duration of the study.
9. Patients with chronic medical conditions that put them at risk for severe dengue, including uncontrolled diabetes mellitus, severe asthma requiring oral steroids, and admission to the hospital in the previous 6 months for cardiac disease
10. Current use of anticoagulant or antiplatelet drugs or documented medical history of bleeding disorders
11. Malabsorption syndrome or other conditions that would interfere with enteral absorption
12. Immunocompromised due to use of immunosuppressive drugs including systemic corticosteroids (inhaled or topical corticosteroids are allowed) or any current disease or immunocompromised due to any current disease or condition
13. Use of P-glycoprotein (P-gp) inducers and inhibitors as described in [Section 5.6.1](#). *Note: hydroxychloroquine and amiodarone are prohibited within 3 months prior to screening and during the study.*

14. Evidence of severe dengue disease including:

- Severe plasma leakage leading to shock or fluid accumulation with respiratory distress
- Severe bleeding (including any subjects with hemoglobin levels <13.0g/dL in males and <11.0g/dL in females)
- Severe organ impairment (e.g., elevated transaminases  $\geq 1,000$  IU/L, impaired consciousness, renal failure [including any subjects with creatinine clearance < 60 mL/min {Cockcroft Gault formula}, or heart impairment] [including any subjects with clinically significant abnormal ECG at Screening])

15. Suspected or confirmed acute illness thought to be caused by a pathogen other than DENV

16. Confirmed or suspected SARS-CoV-2 infection or contact with patients with confirmed SARS-CoV2 infection within 7 days prior to screening

17. ALT or AST > 5x upper limit of normal (ULN) or total bilirubin > 1.5x ULN (Gilbert's syndrome is exempt) or platelet count <80,000/mm^3 at the time of screening

18. Has any other medical disease or condition that in the opinion of the site principal investigator or appropriate sub-investigator, precludes study participation. This includes any acute, subacute, intermittent, or chronic disease or condition that would place the patient at an unacceptable risk of injury, render the patient unable to meet the requirements of the protocol, or interfere with the evaluation of responses or the patient's successful completion of the trial

One-time retests of individual screening laboratory parameters or assessments may be permitted in certain scenarios. Such scenarios may include lab processing error, results inconsistent with subject's historical values/medical history, or other extenuating circumstances such as a recent or intercurrent illness potentially affecting screening laboratory results.

